# 6.2 Secondary endpoint analysis

Not applicable.

# 6.3 Analysis of other efficacy variables

The following other efficacy endpoints will be analyzed for this study:

Insomnia-related endpoints:

- Change from baseline up to Week 2 and Week 4 of the insomnia severity by the ISI©;
- Change from baseline to Week 1, 2, 3, and 4 in quality of sleep VAS, depth of sleep VAS, daytime alertness VAS, daily ability to function VAS;
- Change from baseline to Week 1, 2, 3, and 4 in the mean number of self-reported awakenings (based on the sleep diary);

# Nocturia-related endpoints:

- Change from baseline to Week 1 and Week 4 in number of nocturnal voids assessed using a voiding diary;
- Change from baseline to Week 1 and Week 4 in the time to the first nocturnal void assessed using the voiding diary;
- Change from baseline to Week 1 and Week 4 in the volume of the first nocturnal void assessed using the voiding diary;
- Change from baseline to Week 1 and Week 4 in the total nighttime voiding volume assessed using the voiding diary;
- Change from baseline to Week 1 and Week 4 in number of daytime voids assessed using a voiding diary;
- Change from baseline to Week 1 and Week 4 in the total daytime voiding volume assessed using the voiding diary;

# Quality of life and treatment preference endpoints:

- Change from baseline to Week 4 in lower urinary tract symptoms sub-score using the ICIQ-MLUTS and -FLUTS for male and female subjects, respectively;
- Change from baseline to Week 4 in quality of life relative to nocturia assessed by ICIQ-NQoL;
- Change from baseline to Week 1, Week 2, Week 3, Week 4 in PGA-S and PGI-C for insomnia and for nocturia;
- Change from baseline to Week 2 and Week 4 in quality of life using the EQ-5D-3L;
- Assessment of subjective treatment satisfaction at Week 4 by Numeric Rating Scale;
- Subject preference for treatment;
- Change from baseline to Week 1, Week 2, Week 3, Week 4 in IDSIQ scores (total; alert/cognition; sleepiness; mood).

Analyses of the other endpoints are described below.

# **6.3.1** Analysis of insomnia-related endpoints (ISI®, VAS, number of awakenings) All endpoints will be summarized based on the FAS.

# 6.3.1.1 Insomnia Severity Index©

The ISI© assesses the severity of a subject's insomnia by scoring the severity of sleep onset and sleep maintenance difficulties and any insomnia-related interference with daytime functioning. The assessment is on a 5-point scale (0–4) where the composite score is obtained by summing the 7 rated dimensions measuring the subject's perception of his or her insomnia. The ISI© will be completed by the subject on the eDiary at Visit 1 (baseline), Visit 3 (Week 2, Period 1), Visit 4 (Week 4, Period 1), Visit 7 (Week 2, Period 2), and Visit 8 (Week 4, Period 2).

The change from baseline to Week 2 and Week 4 will be summarized by treatment. Observed values will also be summarized. Changes from baseline to Week 2 and Week 4 will also be analyzed based on an MMRM, as described in Section 6.1.3.

In addition, the proportion of subjects with an ISI© decrease from baseline of greater than or equal to 6 will be summarized, as well as the proportion of subjects with ISI© values of 7 or less at Week 2 and Week 4, by treatment.

# 6.3.1.2 Visual analog scale

The VAS collects information on quality of sleep, depth of sleep, daytime alertness, and daytime ability to function by asking the subjects to report their feelings by placing a mark on a VAS. Self-reported quality of sleep and depth of sleep are assessed in the morning whereas self-reported daytime alertness and daytime ability to function are assessed in the evening. Sleep diaries must be completed daily from Visit 1 to Visit 8.

#### 6.3.1.2.1 Variables

Baseline VAS is defined as the mean value based on the sleep diary entries completed for the 7 days immediately preceding the randomization visit.

For Week 1, the VAS scores are averaged across Days 2–8, for Week 2 across Days 9–16, for Week 3 across Days 17–22, and for Week 4 across Days 23–29 (in both treatment periods). Subjects must have at least 2 days of data during each week to calculate a weekly mean. Otherwise, the mean value will be considered missing for that week.

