3.2.1 SDQ [Appendix 2]

The sleep diary includes a morning and evening questionnaire and four VASs related to the efficacy assessments (and a fifth VAS to collect morning sleepiness, described below in the safety assessment Section 3.3.2). The morning and evening questionnaires collect information on self-reported sleep characteristics (e.g., sTST and other sleep quantitative characteristics), napping, bedtime, and timing of study treatment intake. The VAS collects information on quality of sleep, depth of sleep, daytime alertness, and daytime ability to function by asking the subjects to report their feelings by placing a mark on a VAS. Self-reported quality of sleep and depth of sleep are assessed in the morning whereas self-reported daytime alertness and daytime ability to function are assessed in the evening.

The sleep diary will be uploaded into an electronic hand-held device and given to the subjects at Visit 1. Sleep diaries will be available in the subject's language and must be completed daily from Visit 1 until Visit 8 and at PEOT.

EU CT 2022-501246-30-00

Doc No D-23.307

For further information about the set-up and the use of the sleep diary on the hand-held device, refer to the investigator site electronic Clinical Outcome Assessment study information guide.

Confidential

For assessments that derive from the SDQ, baseline is defined as the average of the 7 days immediately preceding Visit 2. The endpoints will be assessed at Week 1, Week 2, Week 3, and Week 4 using averages of 7 days.

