3.4 Endpoints

It is anticipated that the collection of the voiding volume will interfere with sleep-related endpoints, therefore a staggered approach for the endpoint assessments is pursued. The details are described below and apply for each treatment period.

Information on the endpoints and their relation to the objectives is shown in Table 3.

Further details on the endpoints are described in the SAP.

Table 3Endpoints and objectives

Objectives	Endpoints in period I and period II			
To assess the efficacy of daridorexant on insomnia in subjects with insomnia and	Primary endpoint:Change from baseline to Week 4 in sTST			
comorbid nocturia	Other insomnia related endpoints:			
	• Changes from baseline to Week 1, Week 2, and Week 3 in sTST			
	• Changes from baseline to Week 2 and Week 4 in ISI [©] total score			
	• Changes from baseline to Week 1, Week 2, Week 3, and Week 4 in quality and depth of sleep as determined by scores on the VAS (mm) in the morning			
	• Changes from baseline to Week 1, Week 2, Week 3, and Week 4 in the daytime alertness and daily ability to function as determined by scores on the VAS (mm) in the evening			
	• Changes from baseline to Week 1, Week 2, Week 3, and Week 4 in mean number of self-reported awakenings based on the sleep diary			
To assess the efficacy of daridorexant on	Nocturia related:			
nocturia	• Changes from baseline to Week 1 and Week 4 in number of nocturnal voids assessed using a voiding diary			
	• Changes from baseline to Week 1 and Week 4 in the time to the first nocturnal void assessed using the voiding diary			
	• Changes from baseline to Week 1 and Week 4 in the volume of the first nocturnal void assessed using the voiding diary			
	• Changes from baseline to Week 1 and Week 4 in the total nighttime voiding volume assessed using the voiding diary			
	• Change from baseline to Week 1 and Week 4 in number of daytime voids assessed using a voiding diary			
	• Changes from baseline to Week 1 and Week 4 in the total daytime voiding volume assessed using the voiding diary			
	Change from baseline to Week 4 in ICIQ-NQoL			
	• Change from baseline to Week 4 in lower urinary tract symptoms sub-score using the ICIQ-MLUTS and FLUTS for male and female subjects, respectively			
To assess the overall patient's ratings of their condition and symptoms	• Changes from baseline to Week 1, Week 2, Week 3, and Week 4 in Patient Global Assessment of Disease Severity (daytime symptoms)			

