Daridorexant (ACT-541468) Insomnia and comorbid nocturia Protocol ID-078A401 Version 3

4 September 2023, page 44/122

Objectives	Endpoints in period I and period II			
	• Changes from baseline to Week 1, Week 2, Week 3, and Week 4 in Patient Global Impression of Change (daytime and nighttime symptoms)			
	 Change from baseline to Week 4 in Patient Global Assessment of Disease Severity (daily life) Change from baseline to Week 4 in Patient Global Impression of Change (daily life) 			
	• Change from baseline to Week 2 and Week 4 in EQ-5D-3L score			
	• Treatment satisfaction at Week 4 assessed via NRS			
	• Treatment period preference at Visit 8 (EOTP II)			
To explore a) the sensitivity of the IDSIQ to detect clinical changes in this study population and b) the use of narratives to report subject's perception of treatment effect	 The change from baseline to Week 1, Week 2, Week 3, and Week 4 in all IDSIQ domains The subjects will be asked to complete a narrative at the end of each treatment period. More details on the analysis will be provided in the SAP. 			
To assess the safety and tolerability of daridorexant	Safety endpoints			
	Safety monitoring will include:			
	• Occurrence of TEAEs up to 5 days after EOTP I and/or EOTP II.			
	• Occurrence of treatment emergent AESIs up to 5 days after EOTP I and/or EOTP II.			
	• Occurrence of treatment-emergent serious adverse events up to 5 days after EOTP I and/or EOTP II.			
	Occurrence of TEAEs leading to premature discontinuation of the study and/or treatment.			
	• Change from baseline to EOTP I and EOTP II in vital signs (systolic blood pressure, diastolic blood pressure, and pulse rate).			
	• Change from baseline to EOTP I and EOTP II in morning sleepiness as determined by the scores on the VAS in the morning.			
	• Occurrence of suicidal ideation, suicidal behavior, and/or self-injurious behavior with / without suicidal intent based on the C-SSRS [©] at Visit 1, Visit 4, Visit 5, Visit 8, and Visit 9.			

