## 6.1.1 Primary efficacy endpoint

The primary efficacy endpoint of this study is defined as the change from baseline to Week 4 (of both treatment periods) in sTST.

In each treatment period, the change from baselinea to Week 4b in sTST is calculated as follows:

• Change from baseline = Mean value at Week  $4^b$  – Mean value at baselinea.

Changes from baseline in sTST for Weeks 1–3 will be included in the MMRM. Definitions for the changes from baseline will be identical. For Week 1, sTST is averaged across days 2–8, for Week 2 across days 9–15, and for Week 3 across days 16–22.

Subjects must have at least 2 days of data during each week to calculate a weekly mean. Otherwise, the mean value will be considered missing for that week.

For subjects discontinuing a treatment period prematurely (TP I or TP II), all data up to Day 29 will be included to derive the weekly averages (if data is available up to that point). In the event that subjects have extended treatment periods > 4 weeks, only data up to Day 29 will be included in the derivation of the weekly averages.

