#### 6.3.1.3 Number of awakenings

The number of awakenings is collected daily via a Sleep Diary Questionnaire.

The change from baseline to Week 1–Week 4 in number of awakenings will be summarized by treatment. Observed values will also be summarized by treatment.

Definitions of the weekly averages are the same as described in Section 6.3.1.2.

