#### 6.3.3.5.1 *Variable*

The different IDSIQ domains are derived as shown in Table 5.

Table 5 Insomnia Daytime Symptoms and Impacts Questionnaire description

Domain	Scoring	Minimum/Maximum Score
	Daily: Sum of Item 1*, Item 2*, Item 3, Item 9, Item 10*, Item 14*	Minimum score: 0 Maximum score: 60
Alert/Cognition	Weekly Average: Mean of the daily domain score over 7 days	Higher score: greater burden of illness
Mood	Daily: Sum of Item 4, Item 5, Item 6, Item 7 Weekly Average: Mean of the daily domain score over 7 days	Minimum score: 0 Maximum score: 40 Higher score: greater burden of illness

Page 33/50

Statistical Analysis Plan for Clinical Study Report Version 2 Doc No D-24.149

Domain	Scoring	Minimum/Maximum Score
Sleepiness	Daily: Sum of Item 8*, Item 11, Item 12, Item 13	Minimum score: 0 Maximum score: 40 Higher score: greater burden of illness
	Weekly Average: Mean of the daily domain score over 7 days	
Total score	Daily: Sum of all domains above  Weekly Average: Mean of the daily domain score over 7 days	Minimum score: 0 Maximum score: 140 Higher score: greater burden of illness

\* Item 1, Item 2, Item 8, Item 10, and Item 14 scores are reverse-scored prior to summation.

Baseline is the mean value based on the IDSIQ entries performed at home on the 7 days immediately preceding Visit 2.

Week 1—Week 4 are defined as the mean values based on the IDSIQ entries performed during Days 2–8, 9–15, 16–22 and 23–29 in each treatment period, respectively. In order to calculate baseline and Week 1–Week 4 averages, at least two days of data must be available. Otherwise, baseline and weekly averages are considered as missing.

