# 7.6 Morning sleepiness (VAS)

Morning sleepiness is analyzed as described in Section 6.3.1.2.

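### Two SAP day counts are wrong as written: VAS and awakenings use 8- and 6-day windows for Weeks 2 and 3, and the washout formula overstates drug-free days by 2. The effect is small.

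*SAP*

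**What the plan says.** **Weekly windows.** SAP 6.3.1.2.1 (Variables, visual analog scale) takes Week 1 as Days 2–8 and Week 4 as Days 23–29. Between them it averages "for Week 2 across Days 9–16, for Week 3 across Days 17–22". Two other sections point to this rule. SAP 6.3.1.3 (Number of awakenings) states: "Definitions of the weekly averages are the same as described in Section 6.3.1.2". SAP 7.6 states: "Morning sleepiness is analyzed as described in Section 6.3.1.2".

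Protocol 3.2.1 covers all sleep-diary endpoints and has them assessed from Week 1 through "Week 4 using averages of 7 days". For sTST, SAP 6.1.1 averages "for Week 2 across days 9–15, and for Week 3 across days 16–22". For IDSIQ, SAP 6.3.3.5.1 uses entries made "during Days 2–8, 9–15, 16–22 and 23–29 in each treatment period".

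**Washout.** SAP 5.4.1 defines the washout duration as the TP II treatment start date minus the TP I treatment end date, plus one day. SAP 10.1 makes those dates the earliest and latest dose-intake dates of each period. SAP 5.4.2 handles an interruption, which is also a gap between two doses, by subtracting one day, because a dose is taken on both boundary dates. SAP 10.2 counts the washout from the day after TP I ends to the day before TP II starts. The planned length is 14–21 days (SAP 2; Protocol 4.1.1).

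**The concern.** Both items are derivation rules that a programmer would code as printed. Neither is declared as an intended change: SAP 11.1 reports no changes to the planned analyses, and 11.3 and 11.4 mention neither rule. SAP 1 allows unamended correction only of minor formatting or spelling errors, and a day range is neither.

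For the windows, Weeks 2 and 3 are protocol-listed time points. Table 3 of Protocol 3.4 has "Changes from baseline to Week 1, Week 2, Week 3, and Week 4 in quality and depth of sleep", with similar entries for daytime alertness, ability to function and awakenings. As written, these results would not line up with the sTST and IDSIQ weeks in the same report.

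For the washout, Protocol 4.3 relies on the 14–21 days to avoid carry-over, and the primary model in SAP 6.1.3 has no carry-over or sequence term. The 5.4.1 table, which SAP 11.4 lists as an addition, is the only planned summary of how long the washout lasted. It would misstate that length for every subject treated in both periods.

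**Working it through.** **1. Window lengths.** Length = last day − first day + 1. Midpoint = (first + last)/2.

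| Measure | Week 1 | Week 2 | Week 3 | Week 4 |
|---|---|---|---|---|
| sTST, IDSIQ | 2–8: 7 days, mid 5.0 | 9–15: 7 days, mid 12.0 | 16–22: 7 days, mid 19.0 | 23–29: 7 days, mid 26.0 |
| VAS, awakenings | 2–8: 7 days, mid 5.0 | 9–16: 8 days, mid 12.5 | 17–22: 6 days, mid 19.5 | 23–29: 7 days, mid 26.0 |

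The protocol's 7 days is reproduced for every sTST and IDSIQ week, but not for VAS Weeks 2 and 3. Both rows total 28 days, so no day is lost or counted twice. Day 16 simply moves from Week 3 to Week 2.

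**2. Effect on the weekly mean.** Each midpoint moves 0.5 day. Under a linear trend the mean shifts by 0.5/7 = 0.071 of one week's change. The documents give no VAS slope. If the treatment difference changes by an assumed 1 to 5 mm per week, the shift is 0.07 to 0.36 mm.

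**3. Effect on precision.** With day-to-day correlation r, the variance of an n-day mean relative to a 7-day mean is [r + (1 − r)/n] / [r + (1 − r)/7]. The documents give no r, so a range is shown.

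| Assumed r | Week 2 (n = 8) | Week 3 (n = 6) |
|---|---|---|
| 0 (extreme) | 0.875 (−12.5%) | 1.167 (+17%) |
| 0.5 | 0.984 (−1.6%) | 1.021 (+2.1%) |
| 0.8 | 0.996 (−0.4%) | 1.006 (+0.6%) |

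**4. Washout: the SAP's own example.** SAP 5.4.2 has a last dose on 19 March and a restart on 23 March. Its rule gives 4 − 1 = 3 days, matching the printed result. The 5.4.1 rule on the same dates gives 4 + 1 = 5.

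**5. Washout: a full case.** Take a last TP I dose on 28 March and a first TP II dose on 12 April, 15 days apart.
- SAP 5.4.1: 15 + 1 = 16.
- Days without a dose, 29 March to 11 April: 15 − 1 = 14.
- Dose-to-dose interval: 15.
- EOTP I visit on the morning of 29 March (Protocol 4.1.1) to Visit 6 on 12 April: 14.
- SAP 10.2, if TP I ends on the last-dose date: (start − 1) − (end + 1) + 1 = start − end − 1 = 14.
- SAP 10.2, if TP I ends on the EOT day, 29 March: 30 March to 11 April = 13.

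So 5.4.1 is 2 above the drug-free count, 1 above the dose-to-dose interval, and 2 or 3 above 10.2.

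**6. Reading against 14–21 days.** Reported = drug-free days + 2. True washouts of 12–13 read 14–15, 14–19 read 16–21, and 20–21 read 22–23.

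**7. Adverse-event windows.** SAP 7.2 runs TEAEs to EOT + 5 days and starts washout AEs on washout day 6. With 10.2 as it stands and EOT on 29 March, TEAEs run to 3 April and washout day 6 (day 1 = 30 March) is 4 April. With EOT on 28 March they run to 2 April and day 6 is 3 April. Both cases join without gap or overlap. Starting the washout on 29 March with EOT also on 29 March would put day 6 on 3 April, inside the TEAE window. That is why 10.2 should not be moved.

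**The case against.** The best counter-argument concerns SAP 10.2. For subjects who complete a period, 10.2 runs the period to the EOT day, and SAP 2 ends TP I on the day after the last dose. On that reading 10.2 counts one day fewer than the drug-free days, so it does not support subtracting exactly 1, and changing 5.4.1 alone leaves a one-day difference for completers. This stands as a caveat, and a footnote can record it. It does not rescue the present formula, because it widens the gap from 2 days to 3. The case for subtracting 1 rests mainly on SAP 10.1 and 5.4.2 and on the EOTP I to Visit 6 interval.

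A related point is that 5.4.1 never says its washout means drug-free days, so the figure of 2 depends on that choice of reference. That is fair, but no reading in the SAP gives plus 1.

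It is also true that 5.4.1 plans only a summary and a listing, with no in-range categories. A misreading would arise only when someone compares the table with 14–21 days.

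Finally, the consequences are minor. The VAS and awakenings endpoints are exploratory, one diary day moves between two intermediate weeks, and only sTST at Week 4 is formally tested. This is accepted. It limits the importance of the point, not its correctness.

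**Conclusion.** Both rules are wrong as written and should be corrected, although neither threatens the trial's conclusions.

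For the windows, the VAS and awakenings averages for Weeks 2 and 3 use 8 and 6 days instead of 7 and 7. The expected effect is a shift of about 7% of one week's change (linear trend assumed) and a variance change of roughly 2% or less at an assumed day-to-day correlation of 0.5 or more. Both treatments share the same windows, so no treatment bias is evident. The primary sTST endpoint and all Week 1 and Week 4 windows are unaffected. So is the listed safety endpoint, "Change from baseline to EOTP I and EOTP II in morning sleepiness", although any Week 2 and Week 3 morning-sleepiness summaries made under SAP 7.6 would carry the error.

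For the washout, the reported duration exceeds drug-free days by exactly 2 for every subject treated in both periods, given that SAP 10.1 makes both dates dosing dates. No model and no listed PPS exclusion uses this duration.

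**What to change.** - **SAP 6.3.1.2.1:** set Week 2 to Days 9–15 and Week 3 to Days 16–22. Sections 6.3.1.3 and 7.6 then follow by cross-reference.
- **SAP 5.4.1:** state that washout means drug-free days, and compute it as the TP II treatment start date minus the TP I treatment end date, minus 1. A gap of 14 to 21 drug-free days is then reported as 14 to 21.
- **SAP 10.2 and 7.2:** leave unchanged, because the TEAE and washout AE windows join correctly as they stand. A footnote to the washout table can note that, when EOT is Day 29, the 10.2 period is one day shorter than the drug-free count.

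The cost is two line edits and an optional footnote. No new data are needed.

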## 6.3.1.2.2 *Analysis*

The change from baseline to Week 1–Week 4 in VAS scores will be summarized by treatment. Observed values will also be summarized by treatment. Changes from baseline to Week 1–Week 4 will also be analyzed based on an MMRM, as described in Section 6.1.3.

#### 6.3.1.3 Number of awakenings

The number of awakenings is collected daily via a Sleep Diary Questionnaire.

The change from baseline to Week 1–Week 4 in number of awakenings will be summarized by treatment. Observed values will also be summarized by treatment.

Definitions of the weekly averages are the same as described in Section 6.3.1.2.

# 6.3.2 Analysis of nocturia-related endpoints (time to first nocturnal void; voiding volume; number of nocturnal voids)

The Minze Diary Pod [Bladt 2022] consists of a voiding pod and a voiding diary and uses a derivation from the ICIQ bladder diary, which is a 3-day diary that allows subjects to record urinary frequency, volume voided, urgency and fluid intake (amount and type) [Bright 2014]. The voiding pod will automatically transfer the voiding information (i.e., volume and timepoints) to the voiding diary, and the subjects must provide additional

information (i.e., urgency, and amount and type of fluid intake). The Minze Diary Pod must be completed during the day, and it must be started in the morning, i.e., completion only starts on the first morning after Visit 1, Visit 2, and Visit 6 and lasts for 3 days; the Minze Diary Pod must also be completed for 3 full days immediately preceding Visit 4 and Visit 8. The Minze Diary Pod collects all data for the endpoints time to the first nocturnal void, change in voiding volume (nighttime and daytime) including total voiding volume, and change in number of nocturnal voids.

For all analyses below, 'pod voids' as well as 'manual voids' will be used. Only data from completed cycles will be included in the analysis. Bedtime and waketime were collected by Minze Health. Bedtime is defined as the 'exact time the subject went to sleep', and waketime is defined as the 'exact time the subject woke in the morning', according to Minze Health specifications.

# 6.3.2.1 Time to the first nocturnal void

#### 6.3.2.1.1 *Variable*

The variable derivation follows the approach as used by Minze Health.

The time to first nocturnal void (hours) is derived for each voiding night ('Cycle') separately as follows:

• Time to first nocturnal void (in hours) = Time of first nocturnal void (after bedtime and before waketime) – Bedtime.

Potentially, a date is required for computation of the variable if the bedtime is prior to midnight and the first void is after midnight. In the event of missing information on bedtime and/or waketime, the variable is set to missing and the data will not be included in the analyses defined below.

After derivation of the time to first nocturnal void per night (in hours), the average time to first void will also be computed across the 3 voiding nights (by visit). In the event of missing nights or nights without voids, the average will be computed based on the nights with available data.

In the event of no voiding during any of the 3 consecutive nights, the censoring time is defined as follows:

 Censoring time (in hours) = Maximum (Waketime – Bedtime) during voiding cycle 1, 2 or 3 (by visit).

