# 6.3.2.2 Within-subject comparison of time to the first nocturnal void

#### 6.3.2.2.1 Variable

The time to first nocturnal void is derived as described in Section 6.3.2.1.1 (for Week 1 and Week 4). As each subject receives both treatments, a within-subject comparison of the time to first nocturnal void is performed, separately at Week 1 and Week 4, i.e., the 'preferences' (= longer average duration to first nocturnal void across 3 cycles) are summarized in a  $2 \times 2$  contingency table, as shown in Table 4. If a subject is missing data in one or both treatment periods, this subject's information is considered as missing and will not be included in the analysis. In the event of censored data, i.e., subjects that have no single void in 3 cycles, the preference will be assigned to the period where the subject was censored.

Page 26/50

Statistical Analysis Plan for Clinical Study Report Version 2 Doc No D-24.149

Table 4 Contingency table of preferences

Treatment	preference
Heatinent	preference

Treatment group	TP I	TP II	Total
Daridorexant 50 mg	х	у	x + y
Placebo	Z	a	z + a
Total	x + z	y + a	x + y + z + a

TP I/II = treatment period I/II

From this table it can be derived that (x + y) subjects prefer daridorexant 50 mg, whereas (z + a) subjects prefer placebo. The differences across periods can be observed in the total row (x + z) for TP I; y + a for TP II).

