# 6.3.2.2.2 Analysis

The contingency table is analyzed separately at Week 1 and Week 4 based on the FAS via a 2-sided sign test for matched pairs. A binomial distribution will be used to compute the p-values (2-sided), which will be presented in the table.

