#### 6.3.2.4 Change from baseline in total voiding volume (nighttime and daytime)

Three analyses will be conducted for the change from baseline in total nocturnal voiding volume:

- 1. Nocturnal voiding volume as derived by Minze Health (derived data are provided by Minze Health).
- 2. Derived nocturnal voiding volume, defined as cumulative voiding volume between bedtime and waketime.
- 3. Derived nocturnal voiding volume, defined as cumulative voiding volume between bedtime and waketime, excluding nights with a total voiding volume of 0.

The rationale for the conducted analyses is the partially incorrect labelling of day, night and morning voids in the Minze Health database and nights without any voids. For nights

without any voids, it is unclear whether the data were not collected or if the patient did not void at all.

Analyses for the nocturnal voiding volume **plus** the morning volume will be conducted as well, but only based on data as derived by Minze Health.

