## 6.3.2.5 Change in number of nocturnal and daytime voids

Three analyses will be conducted for the number of nocturnal voids:

- 1. Number of nocturnal voids as derived by Minze Health (derived data are provided by Minze Health).
- 2. Derived number of nocturnal voids, defined as the number of nocturnal voids between bedtime and waketime.
- 3. Derived number of nocturnal voids, defined as the number of nocturnal voids between bedtime and waketime, excluding nights with 0 number of voids.

The rationale for the analysis is the same as described in Section 6.3.2.4.

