## 11.4 Additional analyses to those planned in the study protocol

Baseline disease characteristics summary tables were added for the RND and FAS.

A table summarizing the duration of the washout period was added.

The study discontinuations summary table will also be produced for the FAS.

Analyses for ISI©, VAS scales and IDSIQ scales will be repeated based on an MMRM for the FAS.

An analysis by treatment period was added for the missing data patterns of the primary endpoint and for the compliance summary table.

Two sensitivity analyses each were added for 'Total nocturnal voiding volume' and 'Total number of nocturnal voids' to account for missing and inconsistent data.

For the time to first nocturnal void, a Kaplan-Meier plot was added for all subjects at baseline.

Daridorexant (ACT-5414	168 )
ID-078A401	
30 May 2024	
Page 41/50	

Confidential

Statistical Analysis Plan for Clinical Study Report Version 2 Doc No D-24.149

An analysis was added for the total nocturnal voiding volume plus the morning void volume.

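### Time to first nocturnal void: one or two void-free nights earn no credit, three win outright, and only this endpoint lacks a version that keeps zero-void nights

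*SAP*

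**What the plan says.** SAP 6.3.2.1.1 derives the time from bedtime to the first void for each of three nights and then averages by visit: "In the event of missing nights or nights without voids, the average will be computed based on the nights with available data". Three void-free nights are handled differently: "In the event of no voiding during any of the 3 consecutive nights, the censoring time is defined as follows", namely the longest of the three sleep spans (waketime minus bedtime).

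SAP 6.3.2.2.1 compares the two periods within each subject. The preferred period is the one with the "longer average duration to first nocturnal void across 3 cycles". For censored data the rule is: "subjects that have no single void in 3 cycles, the preference will be assigned to the period where the subject was censored". SAP 6.3.2.2.2 then states: "The contingency table is analyzed separately at Week 1 and Week 4 based on the FAS via a 2-sided sign test for matched pairs". The Kaplan-Meier output in 6.3.2.1.2.1 is descriptive only, so this sign test is the only inference on the variable.

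For the other voiding endpoints the SAP is more cautious. Section 6.3.2.4 says of nights "without any voids, it is unclear whether the data were not collected or if the patient did not void at all". Volume and count therefore each have one version that keeps zero-void nights and one that sets them to missing; for count the latter is described as "excluding nights with 0 number of voids" (6.3.2.5). Section 11.4 records the additions: "Two sensitivity analyses each were added for 'Total nocturnal voiding volume' and 'Total number of nocturnal voids' to account for missing and inconsistent data". For time to first void, the same section adds only a baseline Kaplan-Meier plot.

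**The concern.** The rule reads the same observation in two ways. One or two zero-void nights are treated as missing, while three are treated as real and as the best result. The score therefore does not rise with the number of void-free nights: it stays flat and then jumps to an automatic win.

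If daridorexant produces more void-free nights, the average and the sign test leave most of that benefit out. The mean delay is understated and some subjects are scored for the wrong treatment. The SAP recognises that zero-void nights are ambiguous and protects count and volume against either reading. Time to first void is built from the same nights and has no such protection.

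**Working it through.** **Structure.** The documents state no effect size or power for this endpoint, so there is no figure to reproduce. The SAP average is the sum of (first void − bedtime) over the nights with a void, divided by the number of such nights. The alternative gives each void-free night its sleep span and divides by all evaluable nights. Take a comparator period of 3.5 h on every night, and assume 7.5 h nights:

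| Nights in the other period | SAP average | SAP result | Void-free nights credited | Result |
|---|---|---|---|---|
| 3.0, 3.0, 3.0 | 3.0 h | loses | 3.0 h | loses |
| 3.0, 3.0, none | 3.0 h | loses | (3.0+3.0+7.5)/3 = 4.5 h | wins |
| 3.0, none, none | 3.0 h | loses | (3.0+7.5+7.5)/3 = 6.0 h | wins |
| none, none, none | censored at 7.5 h | wins | 7.5 h | wins |

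**Size under assumed distributions.** Assumptions: Weibull first-void times, a shared subject factor with log-SD 0.35, and three 7.5 h nights per period. Each scenario used 400,000 subjects, split into 8,000 trials of 50 for the two-sided exact sign test. Attenuation is 1 − (SAP difference / credited difference), taken before rounding.

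| Scenario (median, placebo → daridorexant) | Credited | SAP rule | Attenuation | Power, credited vs SAP |
|---|---|---|---|---|
| Shape 1.5, 1.5→2 h | 0.57 h | 0.49 h | 14% | |
| Shape 1.5, 2→2.5 h | 0.52 h | 0.39 h | 24% | 48% vs 35% |
| Shape 1.5, 2.5→3.5 h | 0.88 h | 0.55 h | 38% | 82% vs 51% |
| Shape 1.5, 3→4 h | 0.78 h | 0.43 h | 45% | |
| Shape 1.5, 3.5→5 h | 0.95 h | 0.46 h | 52% | |
| Shape 1, 2.5→3.5 h | 0.71 h | 0.31 h | 56% | |
| Shape 2.5, 2→2.5 h | 0.53 h | 0.50 h | 6% | 91% vs 89% |
| Shape 3, 2.5→3.5 h | 1.00 h | 0.89 h | 11% | |
| 0.5 h shift, shape 1.5, median 2.5 h | 0.47 h | 0.44 h | 7% | 43% vs 41% |
| 1 h shift, shape 1.5, median 2.5 h | 0.93 h | 0.86 h | 8% | |
| 0.5 h shift, shape 2.5 or 3, median 2 h (two scenarios) | 0.50 h | 0.49 h | 1% | |

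In the shape 1.5, 2.5→3.5 h case, the SAP rule moves 8.4% of subjects from daridorexant to placebo preference and 2.5% the other way. Fully void-free visits are 0.2% vs 1.3%. The direction of the mean difference did not reverse in any scenario.

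**Extra void-free nights only.** A separate simulation used the same first-void distribution in both periods (shape 1.5, mean 2.5 h, 7 h nights, 50 subjects, 600 runs) and added void-free nights to one period. With 10%, 20% and 30% extra, the SAP rule gave that period 49%, 49% and 51% of preferences, with rejection about 2% to 3%. Crediting the nights gave 60%, 69% and 77%, with rejection about 26%, 77% and 97%.

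**The opposite error.** Suppose there is no true effect and 5% vs 15% of nights are uncollected. Counting them as void-free produces a false 0.46 h difference and 22% rejection; the SAP rule gives 0.00 h and 3%. At 5% vs 10%, crediting gives 0.23 h and 8%. The SAP rule is exposed too when a whole visit is unrecorded but read as void-free: at 10% or 20% of subjects in one period, it rejects in about 8% or 23% of runs (crediting: about 9% and 24%).

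**The case against.** - **Void-free nights may be rare.** Inclusion criterion 7 (Protocol 5.2) requires an average of at least 2.6 episodes and no screening night with fewer than 2 voids. The shape 1.5, 2.5→3.5 h case implies about 6% void-free nights on placebo and 15% on daridorexant. The 45% to 56% attenuations imply 10% to 15% and 20% to 29%. In the six scenarios that are pure shifts or have under 5% void-free nights on daridorexant, attenuation is at most 11%. This stands: 1% to 56% is not a likely range.
- **Other analyses cover part of it.** The minimum time to first void (SAP 6.3.2.1.1.1) is unchanged by void-free nights whenever any night has a void, and the void-count model includes a version that keeps zeros. Both are true, but the sign test uses the average.
- **Dropping ambiguous nights is defensible.** It protects against the false positive shown above when single nights are uncollected, and restricting analysis to completed cycles (6.3.2) may remove some of these. But 6.3.2.4 still calls zero-void nights ambiguous, and the three-night rule abandons that caution.
- **Crediting averages a censored time as if observed.** Correct. It is not an exact analogue of the count and volume versions, so it belongs beside the current rule and should not replace it.
- **Low stakes.** The protocol defines no secondary endpoints, and only sTST is adequately powered (Protocol 3.5). This bears on priority; the scoring fault remains.

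**Conclusion.** The concern holds. The discontinuity and the missing counterpart follow directly from the SAP text and need no assumption. The practical size is unknown. Under the assumed distributions it runs from negligible (1% attenuation) to large (56%), depending mainly on how often void-free nights occur on treatment. Single subjects can be scored in the wrong direction; reversal at group level is possible but not expected. Neither handling is safe alone, since one can hide a real delay and the other can create a false one. The consequence is limited to an exploratory endpoint, though nocturia is the stated secondary objective and this endpoint carries its own p-values at Week 1 and Week 4. It should be fixed, because the remedy is cheap.

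**What to change.** Before unblinding, keep the current derivation and add a second version to SAP 6.3.2.1.1:

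- Each completed cycle with a bedtime and waketime but no nocturnal void contributes waketime minus bedtime, flagged as censored. The average is taken over all evaluable nights.
- A subject void-free on all nights gets this same average in place of the maximum span. A subject void-free on all nights in both periods counts as a tie, a case 6.3.2.2.1 does not cover.
- Run the descriptive tables and the sign test on both versions, in line with 6.3.2.4 and 6.3.2.5. Kaplan-Meier may use per-night records, descriptively only.
- Report the number of zero-void nights by treatment and visit. If the versions disagree, state that the result depends on how zero-void nights are read.

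The cost is one derivation and one extra set of tables, with no new data. Two downsides belong in the footnote. The new average is a restricted mean that depends on sleep-period length; with nights of 7.0 vs 7.43 h and no void effect, the simulated difference was 0.03 h, against 0.06 h under the current rule. Uncollected nights counted as void-free could also overstate a delay. If the blind is already broken, label the added version post hoc.
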